Self-management online portal. As part of her K-Award, the PI designed a web-based portal and examined the feasibility and preliminary efficacy of a six-week intervention to promote portal use in AYA with SCD aged 16-24. Data from 42 AYAs indicated that 95% found the portal easy to use, 90% found it beneficial, 98% reported that the portal increased SCD knowledge, and 95% reported that it improved their self-management. Yet, outcome data for BA and other measures were not impressive (pretest PAM-13 M=72.0; posttest PAM-13 M=65.6; i.e. no significant reduction in BA) suggesting that online-only interventions were unlikely to lead to measureable behavior change.

In-Person Delivery of SM Intervention for AYAs with SCD. The PI also conducted a pilot study of a six-week in-person group self-management intervention (Chronic Disease Self-Management Program – CDSMP) with 74 AYAs with SCD aged 16-24. Intervention participants were highly satisfied with the CDSMP (9.05 out of 10), yet barriers to regular attendance at sessions posed a strong impediment to study participation. Session completion was defined as 4/6 sessions; 34% of completers attended less than six sessions and another eight participants who started the intervention dropped out due to illness or family issues (e.g. hospitalization, family member ill). Participants rated sessions focused on physical activity and exercise, managing difficult emotions, and communicating with healthcare providers as most beneficial and reported that interacting with other AYA with SCD enhanced their ability to learn and continue to use self-management skills. Multivariate analyses found significant improvement from pre to post on AYA confidence in: 1) using exercise to deal with health problems ( $p = .005$ ), 2) keeping fatigue from interfering with pleasurable activities ( $p = .020$ ), and 3) exercising three times per week ( $p = .057$ ). Study findings are highly promising and suggest that in-person interventions have strong potential to improve AYA self-efficacy for self-management.

In summary, our pilot work underscores the need for multicomponent, peer-based interventions that include easily accessible technology enhanced tools combined with at least some in-person contact to enhance knowledge, peer support, and self-monitoring, but also to produce greater engagement and clinically significant changes in self-management in AYA with

[figure not shown]

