
**Table 2. Intervention Target by Treatment Sessions**

[figure not shown]
Week (Location)	Topics	Behavioral Activation (BA) Target
1 (in-person)	SCD Knowledge, Self-Monitoring, Action Planning	Knowledge, Self-Efficacy, Readiness for Change, Family/Social Support
2 (in-person)	Communication, Problem Solving, Action Planning	Skills, Self-Efficacy, Family/Social Support
3 (online)	Pain Management, Mood Management, Action Planning	Mood, Self-Efficacy, Skills, Family/Social Support
4 (online)	Cognitive Restructuring, Action Planning	Self-Efficacy, Skills, Family/Social Support
5 (online)	Managing Emergencies, Treatment Adherence, Action Planning	Knowledge, Skills, Self-Efficacy, Resources, Family/Social Support
6 (in-person)	Decision Making, SCD Health Behaviors, Action Planning	Skills, Knowledge, Self-Efficacy, Resources, Family/Social Support
Booster (in-person/online)	Review of skills, Progress Updates, Action Planning	Self-Efficacy, Readiness to Change, Family/Social Support

**Attention control arm:** Additional trained therapists (not conducting *SCThrive*) will conduct the attention control intervention which consists of 6 weekly 15-20 minute individual phone calls and a follow-up phone call on the following educational topics: Session 1: What is Sickle Cell Disease?; Session 2: It's in the Genes; Session 3: SCD Complications; Session 4: Treatments for SCD; Session 5: Healthy Living with SCD; and Session 6: Navigating Health Insurance.

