*SCThrive arm.* Four successive groups with four to eight participants per group will be conducted. Participants will receive the finalized six-week *SCThrive* intervention using procedures described in Aim 1. To encourage retention and skill maintenance, participants will receive one online/in-person booster session two weeks after treatment ends. Based on feedback from the Intervention Development Team we will allow participants who cannot attend the in-person session due to illness or other factors to attend online via ZOOM. We will also allow participants to review a missed session recording before the next session with the CRC.

*Attention control arm.* Additional trained therapists (not conducting *SCThrive*) will conduct the attention control intervention which consists of six weekly 15-20 minute individual phone calls via Zoom. Participants will receive one online booster session two weeks after treatment ends.

*Assessment Strategy.* AYAs will complete questionnaires assessing BA, self-management behaviors (including healthy lifestyle behaviors), quality of life, and depressive symptoms (which can impact BA; Beck Depression Inventory-II), at baseline, post-treatment, and six-weeks after treatment (see Table 3). Caregivers or AYAs  $\geq$  age 18 will complete demographic (e.g. parental

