## 9. DATA ANALYSIS/METHODS

**Analytic Plan.** We will use Mplus (Version 7.20) to conduct our analyses. Descriptive statistics (e.g. proportions for dichotomous variables, means, and standard deviations) will be calculated for all measures of interest. Outliers will be examined and kept in final analyses, unless substantial evidence is available for their deletion (e.g., data errors). When testing statistical hypotheses, statistical model assumptions will be examined.

**Aim 1: Determine the feasibility and acceptability of the SCThrive intervention for adolescents and young adults with SCD.** **Feasibility** of SCThrive will be assessed by the proportion of eligible patients approached for the study who consent to participate and attend at least 4/6 sessions. **Acceptability** will be assessed by qualitative analysis of focus groups at the end of treatment. The focus groups will elicit the AYAs overall impression of the program, the mixed format, how well they perform skills, and the progression of activities, as well as content- and format-specific feedback on the integration of iManage and SCD content, interest level, and length of sessions.

**Aim 2: Conduct a pilot randomized trial (final N=54 assuming 15% attrition) to determine whether the refined SCThrive intervention is superior to attention control in improving BA in AYAs with SCD ages 13-21.** A 2 (group; treatment vs. control) by 2 (time; Pre-/Post-test) mixed ANCOVA analysis will be used, with BA (PAM-13) as our primary outcome, time and group as main effects, and a time\*group interaction effect, to determine the needed effect size estimates. The statistical test of the interaction will be the primary tests of the efficacy of the SCThrive intervention. If statistically significant, the group\*time interaction would indicate BA changed differently across time between the two groups and effect sizes (d) will be calculated

for all significant simple main effects and simple comparison effect size calculations described above.

**Exploratory Aim:** A MANOVA will be used to test for significant group (*SCThrive* vs. attention control) differences on improvements in self-management behaviors and quality of life scores at three months. A significant omnibus test will be followed with simple comparisons and computation of effect size estimates (d).

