**Power Analysis:** We chose the PAM-13 (BA) as our primary outcome for power estimates because the General Linear Modeling analyses found a significant improvement in PAM-13 means from pre-test to post-test for the in-person self-management versus the self-management online portal groups, whereas the responsiveness of the other measures (e.g. SCD quality of life) may require a longer time-frame. The average effect size (eta-squared) for the change in BA was  $\eta^2 = 0.14$ , which is a large effect. A 2 (treatment vs. control) by 2 (pre-test, post-test) mixed effects ANCOVA power analysis was conducted using the internal Monte Carlo simulation capabilities of Mplus (Version 1.20) under the following assumptions: 1) the attention control arm will show a  $d = 0.30$  effect size improvement in BA from pre-test to post-test, 2) based on the effect size obtained from pilot data analyses (i.e.,  $\eta^2 = 0.14$ ), the *SCThrive* intervention arm will show a  $d = 0.90$  effect size improvement from pre-test to post-test, 3) participants assigned to the *SCThrive* intervention arm will show an incremental effect of  $(0.90 - 0.30 = 0.60)$   $d = 0.60$  over participants assigned to the attention control arm, and 4) the inclusion of two control covariates (treatment type and baseline healthcare utilization), together with blocking on participant age and disease severity prior to randomization, will explain 40% (i.e.,  $R^2 = 0.40$ ) of post-test BA score variance. Results from the Monte Carlo simulation analyses based on 5,000 simulated datasets showed power will be  $> 0.80$  to detect the  $d = 0.60$  anticipated incremental improvement for the *SCThrive* intervention arm if recruitment,  $N = 64$ , results in a post-attrition  $N = 54$  ( $N = 27$  per group) available for statistical analysis.

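### SCThrive is delivered in four peer groups and the control individually, yet neither the primary arm-by-time ANCOVA nor the power calculation allows for correlation within groups

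*Combined protocol and SAP*

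**What the plan says.** Randomisation is of individuals within age-by-severity cells (Sections 4 and 6). After randomisation the arms are delivered differently. For SCThrive, Section 8 states: "Four successive groups with four to eight participants per group will be conducted". Section 17.3 puts 32 participants in this arm, which four groups can hold only if each has eight. Controls are treated one at a time: Section 4 describes "6 weekly 15-20 minute individual phone calls", and Section 8 says that additional therapists "will conduct the attention control intervention which consists of six weekly 15-20 minute individual phone calls via Zoom".

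The primary analysis in Section 9 is a two-arm layout crossed "by 2 (time; Pre-/Post-test) mixed ANCOVA analysis will be used, with BA (PAM-13) as our primary outcome". Its terms are time, arm and their interaction, and "The statistical test of the interaction will be the primary tests of the efficacy of the SCThrive intervention". The power simulation lists four assumptions: the control-arm change, the SCThrive change, the increment of d = 0.60, and an R² of 0.40 attributed to "the inclusion of two control covariates (treatment type and baseline healthcare utilization), together with blocking on participant age and disease severity prior to randomization".

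Neither passage has a therapy-group effect, an ICC, a design effect or a cluster-robust error. The word mixed refers to the arm-by-time layout. The general undertaking in Section 9 to examine model assumptions names no check for clustering. Alpha, sidedness and a rule for forming groups are not given.

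**The concern.** People who share sessions, peers and facilitators may come to resemble each other in outcome. The trial's own rationale makes this plausible. Sections 3 and 4 present peer support as part of how SCThrive works, and Section 3.1 reports from the earlier in-person programme that "interacting with other AYA with SCD enhanced their ability to learn and continue to use self-management skills". Blocking on age and severity before randomisation cannot remove a correlation that arises afterwards.

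A positive correlation makes the SCThrive mean more variable than the ANCOVA assumes. The primary test then rejects a true null too often, and the sample size supports less power than stated. This matters even in a pilot: Section 2 states superiority hypotheses, Section 9 calculates effect sizes for the effects found significant, and Section 1 says the results will support an application for a fully powered multisite trial. If group membership is not recorded, the analysis cannot be repaired later.

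**Working it through.** **Inputs.** From Section 9: d = 0.60, R² = 0.40, 27 analysed per arm. From Section 8: four SCThrive groups. Assumed: two-sided 5%; analysed groups of 7, 7, 7 and 6; ICC (ρ) of 0.02, 0.05 or 0.10. The ICC is on the residual scale, that is, a share of the variance left after R² = 0.40.

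**Step 1: the plan's own figure.** Residual SD = √(1 − 0.40) = 0.775. SE under independence = 0.775 × √(2/27) = 0.211. Then 0.60/0.211 = 2.85. Power is 0.812 by normal approximation and 0.798 by noncentral t with 52 df. The stated figure therefore reproduces, but only with independent participants, and without a margin.

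**Step 2: clustering in one arm.** The size-weighted mean group size is (3 × 7² + 6²)/27 = 183/27 = 6.78. The design effect in the SCThrive arm is DE = 1 + 5.78ρ; in the control arm it is taken as 1. The ratio of true to planned SE is √((DE + 1)/2). Type I error of the planned test is simulated (1.5 million null trials per cell). Clustering-only power is noncentral t with 52 df, using the true SE.

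| ρ | DE | SE ratio | Type I error, planned test | Clustering-only power |
|---|---|---|---|---|
| 0 | 1.00 | 1.000 | 5.0% | 0.80 |
| 0.02 | 1.12 | 1.028 | 5.6% | 0.78 |
| 0.05 | 1.29 | 1.070 | 6.7% | 0.74 |
| 0.10 | 1.58 | 1.135 | 8.5% | 0.69 |

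With groups of 8, 8, 7 and 4 the type I errors are 5.7%, 6.8% and 8.7%. The last column is power for a test that uses the correct SE. The planned test itself would reject somewhat more often, but only because its type I error is inflated.

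**Step 3: the ICC scale matters.** If covariates remove only individual-level variance, a raw ICC of 0.05 becomes 0.05/0.60 = 0.083 on the residual scale. Then DE = 1 + 5.78 × 0.083 = 1.48, and the SE is about 11% too small rather than 7%.

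**Step 4: cost of a cluster-aware test, kept separate.** Comparing four SCThrive group means with the individual controls (Satterthwaite df) has simulated power 0.72, 0.69, 0.65 and 0.59 at ρ = 0, 0.02, 0.05 and 0.10. Adjusting for baseline PAM-13 and the two covariates of the power section (joint R² of 0.40 assumed), with slope variance carried into the SE, gives 0.69, 0.66, 0.63 and 0.57. At ρ = 0 the loss is 0.80 − 0.69 = 11 points. That is the price of having few groups, not of the omission.

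**Step 5: where the group effect must enter.** In a two-time-point model, a group intercept that is constant over time cancels from the arm-by-time contrast. In 600 simulated trials at ρ = 0.10 the SE with such an intercept was 1.000 times the naive change-score SE. With a group-by-time effect the mean ratio was 1.12, although the variance was estimated as zero in 39% of fits.

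**Step 6: age.** Section 4 provides separate exercises for ages 13-17 and 18-21, so single-age groups are possible. Suppose two groups per age band, no true clustering, and age explaining 5% or 10% of outcome variance. A group-means test that ignores age then has power of roughly 0.62 to 0.64 or 0.53 to 0.56, depending on the simulation set-up, instead of 0.72. Its type I error falls to about 3.4% or 2%. An age difference is being read as clustering, so age has to be in the model.

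**The case against.** The strongest reply is that the ICC may be negligible. The same two-person team appears to run all groups (Sections 4 and 12), half the sessions are online (Table 2), and a missed session can be reviewed from a recording (Section 8). At an ICC of 0.02 type I error is only 5.6%. The study calls itself exploratory, uses the model partly to obtain effect sizes, and leaves full efficacy testing to a later trial. This stands as a limit on importance. It does not supply the missing assumption: the test is still the declared primary test of efficacy, and the stated power has no slack.

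Some stronger readings are tempting but unsupported:

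- A reader might infer that type I error is definitely inflated. That needs a positive ICC, which the documents neither give nor rule out.
- A reader might quote 0.59 or 0.57 as the true power. Those figures combine clustering with the small df of a four-group test.
- A reader might say that the planned confidence interval is too narrow. Section 9 plans a test and effect sizes, and no interval.
- A reader might conclude that the four-means comparison must replace the ANCOVA as primary. In a pilot that is a trade-off, not something the documents require.

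**Conclusion.** The omission is certain; its consequence is conditional. The plan does not say in words that participants are independent. That follows from the listed model terms and from the stated power reproducing only without a design effect.

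With 27 per arm, two-sided 5% and residual-scale ICCs of 0.02 to 0.10, the planned SE is too small by a factor of about 1.03 to 1.135, a nominal 5% test runs at about 5.6% to 8.5%, and clustering takes about 2 to 11 points off the power. The documents do not support treating the trial as invalid or its effect estimate as biased. The point should be fixed because the correction is cheap and part of it cannot be made afterwards.

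**What to change.** 1. Record SCThrive group membership and control-therapist identity. State how groups are formed, including whether they are single-age.
2. Prespecify one cluster-aware analysis of post-test PAM-13, with a group effect in the SCThrive arm only and small-sample df. If the two-time-point model is kept, the effect must be group-by-time. Adjust for baseline PAM-13, treatment type, baseline healthcare utilisation, age band and severity. Enter age as a fixed effect estimated across both arms, because its slope cannot be estimated within single-age groups.
3. State in advance whether this analysis is primary or a sensitivity analysis beside the planned ANCOVA. If the ANCOVA stays primary, make no superiority claim unless the cluster-aware result is reported with it.
4. State alpha and sidedness. Restate power over ICCs from 0 to 0.10, saying whether the ICC is raw or residual, and show the clustering loss and the df loss separately.
5. State two limitations. Four groups estimate an ICC very imprecisely: if the observed F (3 and 23 df) corresponds to an ICC of 0.05, the 95% interval runs from −0.10 to 0.73. Control-therapist clustering is not modelled. An ICC from the earlier in-person programme, run "with 74 AYAs with SCD aged 16-24", would be only a rough guide, since both programme and age range differ.

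The cost is two identifier variables and some wording, with no extra participants. The downside is a stated power below 0.80. The figures of 0.69, 0.66, 0.63 and 0.57 at ICC 0, 0.02, 0.05 and 0.10 apply to a group-means test without age and severity, and must be recomputed once those are added.

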**Table 3. Assessment Strategy**

Construct	Measure	Brief Description/Score Used/ Psychometrics
Primary Outcome Measure		
Behavioral Activation (BA) (AYA report)	PAM-13 	Measures skills, knowledge, confidence and readiness for self-management; Total Score; used in many studies of BA and self-management  ; $\alpha = .87$
Secondary and Exploratory Outcome Measures		
Self-management behaviors (AYA report)	TRAQ-5  ; Youth Risk Behavior Survey items 	Measures managing medications and appointments, tracking symptoms, provider communication, daily interference and physical activity, eating, sleeping and fluid intake; TRAQ Total Score ( $\alpha = .82-.92$ ) and Youth Risk Behavior Survey item mean scores; N/A
Self-management behaviors (clinician rating)	TRxANSIT Scale V4 	Semi-structured interview that assesses knowledge of chronic health condition, medications, adherence, nutrition, self-management skills, insurance, and finding a new health care provider); Knowledge of Chronic Health Condition, Medications, Adherence, Self-Management Skills Subscales; $r = .71$
Medication Adherence (clinician rating)	Medical Adherence Measure (MAM) 	Semi-structured interview with four general modules to assess adherence with medication, diet, exercise, and clinic attendance; Medication Domain; $r = -.40$ ; $r = .89$
SCD-specific quality of life (Caregiver & AYA report)	Peds-QL SCD Module 	Measures several domains of health-related quality of life including pain impact, fatigue, pain management, emotions, communication and treatment adherence; Total Score; $\alpha = .95$
SCD Knowledge (AYA report)	SCD Knowledge Questionnaire 	Measures SCD knowledge including pathophysiology, treatments and self-management; Total Score; $\alpha = .79$
SCD Self-Efficacy (AYA report)	Sickle Cell Self-Efficacy Scale 	SCD self-efficacy scale validated in adolescents with SCD; Total Score; $\alpha = .87$
Self-Regulation (AYA Report)	Treatment Self-Regulation Questionnaire (TSRQ)	Measures the degree of motivation an individual has towards changing/maintaining health behaviors; Total Score; $\alpha > .73$ .
SCD Transition Readiness	Transition Intervention Program Readiness for Transition (TIP-RFT)	Measures healthcare knowledge and skills, education and vocation planning, social support skill set, and independent living skills.
SCD Readiness to Change (AYA report)	SCD Readiness to Change for Self-Management Scale 	Measures amount of prior thought, knowledge, interest, anticipated difficulty and perceived importance about self-management; Mean Scores; N/A
Covariates		
Medical Covariates (EMR review)	Medical Background Case Report Form	ER visits, Hospitalizations, Treatment type
Demographic Covariates (AYA or Caregiver)	Demographics Form	AYAs age, gender, SES, SCD type, parental education, family income level
Treatment barriers (AYA or Caregiver)	Barriers to Care Questionnaire (BCQ) 	Sociobehavioral factors that interfere with successful interaction with the health care system

Table 3. Assessment Strategy		
Construct	Measure	Brief Description/Score Used/ Psychometrics
Psychosocial barriers (AYA or Caregiver)	Psychosocial Assessment Tool 74,95*	Assesses level of psychosocial risk for families of patients with a chronic illness
Feasibility & Acceptability		
Feasibility/ Acceptability/ Satisfaction (AYA report)	SCThrive Feasibility & Acceptability SCThrive Satisfaction Survey SCThrive Follow-up Questionnaire SCHealthED Feasibility & Acceptability	AYA opinion regarding the format, content, satisfaction and usefulness of SCThrive and SCHealthED
Feasibility/ Acceptability/ Satisfaction (AYA report)	iManage Feasibility & Acceptability Survey iManage Usage Survey	App characteristics, usefulness and computer/internet use
iManage Usability	Internet Background Questionnaire & Post Questionnaire	Assesses usability of the iManage app
SCThrive Group Qualitative Interview	SCThrive Feasibility Interview	Assesses usefulness and satisfaction with SCThrive in an interview format

\*Psychosocial Assessment Tool: Patients complete this annually during clinic visits in hematology. We will get permission from participants to use this data. We will only administer it if it has not been completed in the last 12 months. To decrease participant burden, we will then provide the PAT data to the clinic (so the participant will not have to complete it again – see consent form).

**Independent evaluators.** Trained independent evaluators blinded to treatment assignment (doctoral psychology graduate students) will administer self-management and treatment adherence measures (clinician ratings); one evaluator will review 25% of intervention sessions for fidelity.

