***SCThrive Intervention:*** SCThrive consists of six weekly group sessions. Three sessions will be held in-person at CCHMC while the other three will be held online via Skype for Business or Zoom™, group video chat programs. To promote engagement during video chats, therapists will call AYAs by name to join in discussions and brainstorm consistent with the intervention. In addition, AYAs will designate another individual (most likely their caregiver) to receive reminders about their action plans. Two therapists (doctoral level clinical psychologists or graduate students) trained in delivering *SCThrive* and in cultural sensitivity will co-facilitate all sessions (see Table 2 for information on Intervention Sessions). *SCThrive* incorporates several components of culturally-sensitive clinical interventions with African-Americans including its emphasis on becoming an active member of the healthcare team (advocacy), assessment of stress related to SES and ethnic minority status (PAT 2.0), flexible and home-based design, and inclusion of culturally-relevant content (AYA with SCD co-designed *iManage*; use of culturally sensitive and age appropriate book on SCD management, *Hope and Destiny Jr.*; developmentally appropriate scenarios/exercises for the 13-17 and 18-21 age groups). Participants will also receive the *Living a Healthy Life with Chronic Conditions* book. The *iManage* app is accessible on smartphone or tablet; it is an essential component of the intervention because it: 1) visually reinforces the connection between SCD symptoms and self-management behaviors; 2) provides visual feedback on self-management goal progress; 3) facilitates peer support for self-management; and 4) allows AYA to track daily pain, fatigue and mood symptoms. We will ask participants in the first three SCThrive groups to participate in usability testing to ensure the *iManage* app is easy to navigate and that that is it having the desired result. Pilot group participants reported that they would need the ipad to log on for the 8th session so we changed the 8th session to an in-person session so they could turn in their ipads at that session. Since feedback from the pilot group was so informative and beneficial, we have asked two young adults from the pilot group to participate as members of the Intervention Development Team (we will enroll up to 4 to ensure that at least 2 can attend meetings regularly). They will be responsible for advising on study recruitment and retention, study procedures and dissemination of study results. They will be compensated for their participation and sign a consent form. These team members will also be asked to pilot accelerometers to evaluate whether they would be a value add to the SCThrive intervention and should be incorporated in future iterations (next grant application). They will be asked to sign an accelerometer use agreement.

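### An evaluator described as blinded may also review a quarter of intervention sessions for fidelity, which would reveal the arm and could bias two clinician-rated secondary measures

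*Combined protocol and SAP*

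**What the plan says.** Assessor blinding is described in one place, the paragraph on independent evaluators that follows Table 3 in section 8. It opens: "Trained independent evaluators blinded to treatment assignment (doctoral psychology graduate students) will administer self-management and treatment adherence measures (clinician ratings". After a semicolon the same sentence continues: "one evaluator will review 25% of intervention sessions for fidelity". It does not say whether this is one of the raters or someone else, when the review takes place, or how many evaluators there are.

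Table 3 lists two clinician-rated measures, TRxANSIT and the Medical Adherence Measure. Both are semi-structured interviews and both appear among the secondary and exploratory outcomes. The primary outcome, PAM-13, is reported by the participant.

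On delivery, section 4 states that "SCThrive consists of six weekly group sessions" and, for the video sessions, that "therapists will call AYAs by name to join in discussions and brainstorm". Section 8 adds: "Four successive groups with four to eight participants per group will be conducted". Control participants receive six weekly individual calls of 15-20 minutes on educational topics (sections 4 and 8).

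**The concern.** Blinding of a rater protects the outcome only while the rater does not know the arm. A person who watches an SCThrive session learns that everyone in it is in SCThrive. The two arms differ in format and in content, so hearing a control call would be just as informative. If that person later interviews the same participants, the ratings are no longer blinded, although the protocol would report them as such.

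Both measures leave room for rater judgement, and they are the only outcomes for which the documents state blinded assessment. Section 9 plans an exploratory MANOVA on self-management behaviors and quality of life, with effect sizes, and the abstract says the results are to support an application for a fully powered multisite trial. TRxANSIT falls under self-management behaviors in Table 3. The Medical Adherence Measure is listed under a separate construct, and the plan does not say whether it enters the MANOVA.

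**Working it through.** **The plan's own design figure.** Section 9 gives power above 0.80 for PAM-13 with 27 per group, d = 0.60 and R² = 0.40. Alpha is not stated; I assume 0.05, two-sided. The noncentrality is (0.60/√0.60) × √(27/2) = 0.775 × 3.674 = 2.846, and power is Φ(2.846 − 1.960) = 0.812. A noncentral t with 48 df gives 0.796. The stated figure is therefore reproduced to within rounding. No evaluator scores PAM-13, so nothing below changes it.

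**Can the roles overlap?**
- Section 8 names the blinded raters and then, in the same sentence, an evaluator who reviews sessions.
- No section makes the reviewer a separate person, bars the reviewer from rating, or delays the review until ratings are complete.
- Baseline assessment comes before randomization (section 4), so only post-baseline ratings can be affected.
- Groups run one after another (section 8), and the team checks treatment integrity at monthly meetings (section 14). This suggests, but does not prove, that review happens while ratings continue.
- SCThrive participants complete the post-assessment on the day of their last session (section 17.3). Any review of sessions 1-5 carried out during treatment would precede that rating.

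**How many sessions are reviewed?** 4 groups × 6 sessions = 24, and 0.25 × 24 = 6.

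**Chance that a given group is seen at least once, if the 6 are drawn at random:**

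1 − C(18,6)/C(24,6) = 1 − 18,564/134,596 = 0.862.

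If boosters are counted as a seventh session for each group, 7 of 28 are reviewed: 1 − C(21,7)/C(28,7) = 0.902. If the 6 reviews are deliberately spread over the groups, all four are seen.

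**From groups to participants.** Being in a group that is seen is not the same as being present. For a participant who attends 4 of 6 sessions (the attendance criterion for feasibility in section 9), the chance of being present at a reviewed session is 1 − C(20,6)/C(24,6) = 1 − 38,760/134,596 = 0.712. With full attendance it is 0.862.

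**If control calls also count as intervention sessions.** 32 participants × 6 calls = 192, and 25% is 48. The chance that a given control participant is heard at least once is 1 − C(186,48)/C(192,48) = 0.827. This reading exposes control participants as well.

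**Share of ratings and possible bias.** The documents give neither the number of evaluators nor the timing. As an illustration only, suppose k evaluators share the ratings equally, review precedes rating, attendance is full, and an unblinded rater shifts SCThrive scores by b SD. The spurious arm difference is then b × 0.862/k. For k = 4 and b = 0.2 it is 0.04 SD; for k = 2 and b = 0.8 it is 0.35 SD. It is zero if review follows the ratings. Both k and b are assumed, so this range is not an estimate.

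**The case against.** The strongest reply is that the sentence does not say the reviewer also rates Aim 2 participants. It could mean an evaluator assigned to fidelity alone, and the protocol does separate roles elsewhere: control-arm therapists do not deliver SCThrive. Recordings exist (sections 8 and 15), so review could follow the ratings. This stands as far as it goes. The overlap is permitted by the text, not stated in it. But no passage supports the separate-person reading either, and the blinding claim depends on it.

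Several stronger inferences are tempting and do not hold:

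- *All 32 SCThrive participants are unmasked.* This needs each of them to attend a reviewed session. Section 3.1 reports incomplete attendance in the earlier in-person pilot, and the protocol mentions calling participants by name only for the video sessions, which are three of the six.
- *A fixed fraction of clinician ratings, such as a third or a half, is unblinded.* The number of evaluators and how they share the work are not given, and baseline ratings cannot be affected.
- *The trial loses its one safeguard against self-report bias.* In these interviews much of the content comes from participants who know their arm. A blinded rater limits rater bias but does not remove participants' own reporting bias. Emergency visits and hospitalizations are also taken from the medical record, although Table 3 lists them as covariates.

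It is also fair to say that separating the roles would not guarantee blinding. Participants may disclose their arm in the interview, and the same-day post-assessment in SCThrive could signal it to any evaluator. That limits what the change can achieve. It is no reason to leave open a route to unblinding that the plan itself creates.

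**Conclusion.** The concern holds in a limited form. Followed as written, the plan allows a rater it calls blinded to learn the allocation of many SCThrive participants before rating them. Under random sampling of 6 of 24 sessions, each group has about an 86% chance of being seen at least once. This rests on four groups, six sessions each, and a 25% sample of SCThrive sessions. For unblinded ratings to result, the reviewer must also be one of the raters and must review before rating; the first is the natural reading and the second is not stated.

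The consequence is possible rater bias of unknown size in TRxANSIT and the Medical Adherence Measure. A reader might infer that the main result is compromised. It is not: PAM-13 is participant-reported, and its analysis and power do not involve the evaluators. Only 14 per arm are followed to six weeks after treatment (section 4), so far fewer than 32 per arm have a follow-up rating at risk. The severity is low to moderate, and the change is worth making because blinding lost during the trial cannot be restored.

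**What to change.** Add one sentence to the paragraph on independent evaluators. Either:

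- the evaluator who reviews sessions for fidelity does not administer or score TRxANSIT or the Medical Adherence Measure for Aim 2 participants after randomization; or
- that evaluator reviews recordings only after all of their own outcome ratings are complete and locked.

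The first option needs no new staff if there are at least two evaluators, as the plural implies, and costs a little scheduling flexibility. The second relies on recordings and delays feedback on fidelity. If the reviewer was always meant to be a separate person, saying so is enough. It would also help to record any unblinding of a rater, since participants may still disclose their arm.
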